#### 3.4.2.2 Vaccine virus shedding

Titer of vaccine virus shedding evaluated by RSVt qRT-PCR in nasal swabs after each vaccination will be summarized at each timepoint (D01, D04, D08, D11, D15, D18, D22, D64, and D71) in pediatric participants by study intervention group with 95% CIs:

- Number and percentage of participants with detected shedding ( $\geq$ LOD) at each timepoint
- Number and percentage of participants with quantified shedding ( $\geq$ LLOQ) at each timepoint

In addition, titer of vaccine virus shedding will be summarized using descriptive statistics as presented in [Table 3.1](#).

Viral shedding analyses will be performed on the SafAS.

#### 3.4.2.3 Vaccine virus stability

Presence of any vaccine virus variation will be described in pediatric participants receiving placebo and ad-hoc close contact participants:

- Number and percentage of participants with any variation in genetic sequence of ΔNS2, Δ1313, and I1314L segment of the vaccine virus compared to the reference strain vaccine virus isolates in the nasal swabs with detected vaccine virus (vaccine virus shedding by qRT-PCR  $\geq$  LOD).

Vaccine virus stability analysis will be performed on the SafAS .

The vaccine virus stability will be described as well in a random subset of pediatric participants receiving RSVt vaccine based on SafAS.

In order to organize the segment sequencing, a listing of samples to be sequenced is to be provided to the laboratory. The laboratory personnel must remain blinded therefore there should be no mention of the vaccine group in this listing. The nasal swab samples to be tested will be selected as follows:

- Any nasal swab with detected vaccine virus from a participant who received placebo at the previous vaccination and from ad-hoc close contact participants.
- The latest post-vaccination 1 nasal swab with detected vaccine virus among a subset (selected randomly) of 20 participants who received RSVt vaccine at the 1st vaccination and with detected vaccine virus in at least 1 nasal swab.  
Note: a subset of 10 participants randomly selected as defined above among the participants involved in the first interim analysis will be part of the first interim analysis
- The latest post-vaccination 2 nasal swab with detected vaccine virus in any participants who received RSVt vaccine at the 2nd vaccination and with detected vaccine virus in at least 1 nasal swab.

### **3.4.3 Secondary Endpoints**

#### **3.4.3.1 Immunogenicity**

RSV A serum neutralizing antibody titers and RSV serum anti-F IgG antibody titers will be summarized at each timepoint (D01, D57, and D85) in pediatric participants by study intervention group, including but not limited to:

- GMTs and 95% CI
- Geometric mean titers ratio (GMTR) relative to pre-vaccination titer and 95% CI.
- Number and percentage of participants with pre-vaccination titers  $<$  LLOQ or  $\geq$  LLOQ
- Number and percentage of participants with post-vaccination titer  $\geq$  2-fold rise or 4-fold rise
- Reverse cumulative distribution curves (RCDCs)

Immunogenicity analyses will be presented on the FAS.

### 3.4.3.2 Safety

The following safety parameters will be described after each and any vaccination in pediatric participants by study intervention group with the 95% CIs of point estimates. SafAS will be used for analysis.

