9.3.3 Secondary Endpoints

Immunogenicity

The following immunogenicity endpoints will be summarized at each timepoint (D01, D57, and D85) in pediatric participants by study intervention group with 95% CIs: RSV A serum neutralizing antibody titers and RSV serum anti-F IgG antibody titers. The 95% CIs for the GMTs and GMTRs will be calculated using a normal approximation of log-transformed titers. The 95% CIs for the proportions will be based on the Clopper-Pearson method.

Safety

The safety parameters, including frequencies of immediate reactions, solicited reactions, unsolicited AEs, AESIs, MAAEs, and SAEs will be described after each and any study intervention administration in pediatric participants by study intervention group with the 95% CIs of point estimates calculated using the exact binomial distribution (Clopper-Pearson method) for proportions.

Vaccine virus transmission

Presence of vaccine virus detected by RSVt qRT-PCR in nasal swabs after the second study intervention administration (D64 and D71) will be summarized in pediatric participants receiving placebo with 95% CIs:

- Number and percentage of participants with vaccine virus detected at each timepoint
- Number and percentage of participants with vaccine virus detected in at least one nasal swab

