## 1 Overall Design

In the context of intranasal administration of a live attenuated Respiratory Syncytial Virus (RSV) vaccine and to demonstrate that a large-scale study with the RSVt vaccine can be conducted safely, both the transmission rate and the genetic stability of the vaccine virus will be determined. In addition, the vaccine virus shedding will be described in the RSVt vaccinees at regular timepoints and the clinical safety in their close contacts will be assessed.

Data generated in the VAD00014 study will provide insights into the transmission of the RSVt vaccine virus and genetic stability, along with the safety and immunogenic profile of the RSVt vaccine candidate, and may support the next steps of the development, including the planned large-scale Phase III efficacy study.

The design of the study is summarized in [Table 1.1](#) and in [Figure 1.1](#):

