**Table 1.1: Design**

Type of design	Parallel, multi-center
Phase	II
Control method	Placebo-controlled
Study population	

Pediatric participants: Healthy infants / toddlers 6 to < 24 months of age in close contact with other infants / toddlers 6 to < 24 months of age who will participate in the study

Ad-hoc close contact participants: Ad-hoc close contact children and adults who experience acute respiratory illness (ARI) in the 28 days following the administration of the study intervention to the close contact pediatric participant

Level and method of blinding	Observer-blind: 

Blinding for study intervention group assignment: participants, parents or legally acceptable representative (LAR), outcome assessors, investigators, laboratory personnel, Sponsor study staff

No blinding for study staff who prepare and administer the study interventions

Study intervention assignment method	Pediatric participants will be screened for eligibility criteria at the time of inclusion and randomized to receive either RSVt vaccine or placebo in a 1:1 ratio. Randomization will be stratified by contact group (the household /group attended in daycare center) and by age group (< 12 months / ≥ 12 months)

Number of participants	100 pediatric participants 6 to < 24 months of age
Intervention groups	Eligible pediatric participants will be randomized in a 1:1 ratio to receive 2 intranasal administrations (56 days apart) of either the RSVt vaccine or placebo at D01 and D57
Total duration of study participation	Approximately 8 months for each pediatric participant. The duration of the ad-hoc close contacts will be limited to the Illness Visit.
Countries	United States and Puerto Rico
Use of an Independent Data Monitoring Committee, Dose Escalation Committee, or similar review group	NO

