### 3.2 Sample Size Determination

No sample size calculation was done as there are no statistical hypotheses in this study. A total of 100 pediatric participants (ie, 50 per study intervention group) are planned to be enrolled, based on clinical feasibility.

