**Table 3.1: Descriptive statistics produced**

Disposition and follow-up description	Categorical data	Number of participants. Percentage of participants.
	Continuous data	Mean, standard deviation, quartiles, minimum, and maximum.
Baseline characteristics	Categorical data	Number of participants. Percentage of participants.
	Continuous data	Mean, standard deviation, quartiles, minimum and maximum.
Clinical safety results	Categorical data	Solicited: Number and percentage (95% CIs) of participants. Unsolicited: Number and percentage (95% CIs) of participants and number of events.
Vaccine virus shedding results	Categorical data	Number and percentage (95% CIs) of participants.
	Continuous data	Mean and standard deviation, quartiles, minimum, and maximum.
Transmissibility results	Categorical data	Number and percentage (95% CIs) of participants.
Vaccine virus stability	Categorical data	Number and percentage (95% CIs) of participants.
Immunogenicity results	Categorical data (cutoff)	Number and percentage (95% CIs) of participants.
	Continuous data (titer / data)	Log10: Mean and standard deviation. Anti-Log10 (work on Log10 distribution, and anti-Log10 applied): Geometric mean, 95% CI of the geometric mean, quartiles, minimum, and maximum. Graphical representation by Reverse Cumulative Distribution Curve (RCDC)
Infectivity results	Categorical data	Number and percentage (95% CIs) of participants.
RSV WT infection	Categorical data	Number and percentage (95% CIs) of participants, number of events, and 95% CI.

The statistical methodology will be based on the use of two-sided 95% confidence intervals (CI).

All endpoints will be summarized by study intervention group. For the main parameters, 95% CI of point estimates will be calculated using the normal approximation for quantitative data and using the exact binomial distribution (Clopper-Pearson method) for proportions.

For immunogenicity data, assuming that Log10 transformation of the titers/titers ratio follows a normal distribution, at first, the mean and the 95% CI will be calculated on Log10 (titers/titers ratio) using the usual calculation for normal distribution (using Student's t distribution with n-1 degree of freedom), then antilog transformations will be applied to the results of calculations, in

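### Safety is planned as separate per-arm intervals only; a descriptive RSVt-minus-placebo risk difference with a 95% interval should be added

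*SAP*

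**What the plan says.** SAP 3.4.3.2 states that the safety parameters "will be described after each and any vaccination in pediatric participants by study intervention group with the 95% CIs of point estimates". Under SAP 3.4.1, intervals for proportions are computed "using the exact binomial distribution (Clopper-Pearson method) for proportions", and Table 3.1 lists numbers and percentages with 95% CIs for solicited and unsolicited events. Protocol 9.3.3 has the same plan: "by study intervention group with the 95% CIs of point estimates calculated using the exact binomial distribution (Clopper-Pearson method) for proportions". No risk difference, ratio or other between-arm interval is planned for safety. The blacked-out exploratory sections are unlikely to hold one, since SAP 4.1.4 says there are no exploratory safety endpoints.

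Three other passages bear on this:
- Protocol 4.1 says the placebo group allows both transmissibility and safety of RSVt to be assessed under blinding.
- Protocol 10.2.1 and SAP 3.4.6.1.2 treat all solicited systemic reactions as related to the product. The protocol adds that this holds even where another cause is evident.
- SAP Table 1.1: "Randomization will be stratified by contact group (the household /group attended in daycare center"), and also by age group.

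The analysis is declared descriptive, with no hypothesis. On size, SAP 3.2 says: "A total of 100 pediatric participants (ie, 50 per study intervention group) are planned to be enrolled, based on clinical feasibility".

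**The concern.** A per-arm interval bounds the total event rate in that arm: background illness plus any effect of the vaccine. Solicited reactions are collected for 21 days after each dose, in infants who share homes or daycare rooms, so background colds, fever and irritability may supply much of the rate. Because attribution to the product is automatic, only the contrast with placebo can remove that background, and the plan does not estimate it.

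The safety tables therefore cannot say how large a vaccine excess the data are compatible with. Safety data to day 22 are to be shared with Health Authorities before phase III (SAP 3.5). Someone comparing two columns may take overlapping intervals to mean similar safety, and overlap of two 95% intervals is a much blunter comparison than a 95% interval on the difference.

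**Working it through.** The documents give no power, effect size or event rate for safety, so there is no planned figure to reproduce.

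**Inputs from the documents:** 50 per arm (SAP 3.2); two-sided 95% Clopper-Pearson interval in each arm (SAP 3.4.1).

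**Assumptions:** a true excess of 20 points; placebo rates as tabulated; children independent; no dropout.

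**Method.** For every pair of counts (a in RSVt, b in placebo, each 0 to 50), weight by Bin(a; 50, p0 + 0.20) × Bin(b; 50, p0) and sum the weights where the excess is missed. Two definitions of a miss are used:
- Overlap: the RSVt Clopper-Pearson lower limit does not exceed the placebo Clopper-Pearson upper limit.
- Difference: the lower limit of the Newcombe 95% interval for RSVt minus placebo is not above 0.

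| Placebo vs RSVt | Missed by overlap | Missed by difference interval | Gap (points) |
|---|---|---|---|
| 2% vs 22% | 40.7% | 9.0% | 31.7 |
| 5% vs 25% | 56.7% | 17.6% | 39.1 |
| 10% vs 30% | 68.4% | 27.7% | 40.7 |
| 20% vs 40% | 78.9% | 40.5% | 38.4 |
| 30% vs 50% | 82.2% | 45.4% | 36.8 |
| 40% vs 60% | 82.1% | 45.7% | 36.4 |
| 50% vs 70% | 82.2% | 45.4% | 36.8 |

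The gap is the part due to the reporting format. The third column is what 50 per arm cannot resolve. By the usual two-proportion formula, 80% power for a 20-point excess needs 62, 82, 93 and 97 per arm at placebo rates of 10%, 20%, 30% and 40%. With 45 per arm (10% loss, assumed), the overlap miss is 74.9%, 82.0% and 86.4% at placebo rates of 10%, 20% and 40%.

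**Two worked tables.** Newcombe's limits combine the Wilson limits of each arm: lower = d − √[(p1 − l1)² + (u2 − p2)²], upper = d + √[(u1 − p1)² + (p2 − l2)²]. The Wilson limits are 0.191 to 0.438 for 15/50 and 0.366 to 0.634 for 25/50.
- 25/50 vs 15/50: the Clopper-Pearson intervals, 35.5% to 64.5% and 17.9% to 44.6%, overlap. The difference has lower limit 0.20 − √(0.134² + 0.138²) = +0.8 points and upper limit 0.20 + √(0.134² + 0.109²) = +37.2 points, which excludes 0.
- 15/50 vs 15/50: the columns look identical. The difference is 0 ± √(0.109² + 0.138²) = ±17.5 points.

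**Sparse rows.** For 0/50 vs 0/50 the Wilson upper limit is (3.84/50)/(1 + 3.84/50) = 7.1%, so the difference interval is ±7.1 points. The Clopper-Pearson upper limit is also 7.1%, so here the new column adds little.

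**Matching, as an illustration only.** With 50 pairs, one child per arm, equal rates p and within-pair correlation ρ, the half-width is about 1.96 × √[2p(1 − p)(1 − ρ)/50]. At p = 0.30 this is 1.96 × √0.0084 = 18 points for ρ = 0 and 1.96 × √0.00504 = 14 points for ρ = 0.4. The documents give no ρ. For binary outcomes at 30% and 50%, ρ cannot exceed (0.30 − 0.15)/√(0.21 × 0.25) = 0.65; at 20% and 40% the ceiling is (0.20 − 0.08)/√(0.16 × 0.24) = 0.61.

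**The case against.** **No overlap rule exists.** Neither document says safety will be judged by overlap of intervals. A reader might infer a flat 80% miss rate as a property of the plan, but the documents do not support that. The figure depends on a reading habit and on a placebo rate of roughly 20% to 60%. Under a looser reading, where an excess counts as seen if the placebo percentage falls below the RSVt interval, the miss is 12%, 22% and 30% at placebo rates of 10%, 20% and 40%. This stands, and the figures are conditional.

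**The trial is not set up to prove vaccine safety.** A reader might take the words "to demonstrate that a large-scale study with the RSVt vaccine can be conducted safely" in SAP section 1 as a safety claim that the tables must support. The rest of that sentence ties the aim to transmission rate and genetic stability. Safety in vaccinees is a secondary, descriptive objective. This stands. But a difference with an interval is itself a descriptive estimate and needs no hypothesis or margin.

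**Harm can be judged in other ways.** The SAP also reports causality for unsolicited events, intensity, onset, duration and SAE outcome; an internal committee reviews blinded safety data (Protocol 10.1.5); and anyone can compute an unmatched difference from the published counts. True, but for solicited systemic reactions causality is fixed by convention, and none of these outputs states the excess.

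**Interference.** Groups are chosen to make transmission likely, and vaccine virus in placebo children is the primary transmission endpoint (SAP 3.4.2.1). If a fraction t of placebo children acquired the virus and suffered the full excess d, the observed difference would be d(1 − t). This is the strongest objection to resting the safety conclusion on the upper limit of the difference, and it stands. The RSVt arm's own rate is not diluted in this way.

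**Matching gains are uncertain.** Groups may be larger than two, and stratifying by age as well does not guarantee one child per arm in each group. This stands too. Nor can background illness be put down to RSV season as a fact: Protocol 4.2 says the season's effect is hard to judge.

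**Conclusion.** The point holds as a gap in reporting. The plan randomises a placebo group partly to assess safety, counts all solicited systemic events as vaccine-related, and then provides no estimate of the excess over placebo. For a reader who compares intervals by eye, the format adds about 36 to 41 percentage points to the chance of missing a 20-point excess at placebo rates of 10% to 50%. The remaining miss of about 28% to 46% comes from 50 per arm and no table format removes it.

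These figures rest on assumed event rates, independent children and full follow-up; clustering within contact groups could change them. They matter for common events and much less for rare rows such as SAEs. The gap does not invalidate the planned per-arm summaries. It is a cheap improvement that should be made.

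**What to change.** In SAP 3.4.3.2 and Table 3.1, with matching words in Protocol 9.3.3 at the next amendment:
- Keep the per-arm Clopper-Pearson intervals.
- Add the RSVt-minus-placebo risk difference with a two-sided 95% CI for any solicited reaction, fever, Grade 3 solicited reaction, unsolicited AE, MAAE, AESI and SAE, over the periods already planned.
- Account for contact group where the model can be fitted (for example GEE with identity link, exchangeable correlation and contact group as cluster). Use a Newcombe or Miettinen-Nurminen interval where events are sparse.
- Label the intervals as descriptive and unadjusted for multiplicity.
- State that transmission of vaccine virus to placebo children in the same contact group could bias the difference toward zero, so it is read with the RSVt per-arm rate and its upper limit is not by itself the safety conclusion.
- If a gain from matching is mentioned, present it as an illustration that depends on an unknown correlation.

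The cost is SAP wording and one table column, with no new data or participants. The downsides are about 20 unadjusted intervals (six rows over three periods, plus SAEs over their two) and upper limits that look less favourable than side-by-side percentages.

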#### ***Solicited Reactions***

Number and percentage of participants with:

- Presence of solicited administration site reactions and systemic reactions occurring up to 21 days after each and any vaccination
- Each solicited reaction according to time of onset, maximum intensity, and number of days of occurrence and action taken
- Any solicited reaction leading to study discontinuation

#### ***Unsolicited Events and Reactions***

Number and percentage of participants with:

- Any unsolicited immediate systemic event in the 30 minutes after any vaccination according to System Organ Classes (SOC) and Preferred Terms (PT)
- Any unsolicited event and reaction 28 days after each and any vaccination according to SOC and PT
- Any unsolicited event/reaction according to time of onset, maximum intensity, and duration
- Any unsolicited event/reaction leading to study discontinuation

#### ***AESIs***

Number and percentage of participants with:

- Any AESI within 28 days after each and any vaccination according to SOC and PT

#### ***MAAEs***

Number and percentage of participants with:

- Any MAAEs within 28 days after each and any vaccination according to SOC and PT

#### ***SAEs***

Number and percentage of participants with:

- Any SAE within 28 days after any vaccination according to SOC and PT, seriousness, and outcome
- Any SAE throughout the entire study according to SOC and PT, seriousness, and outcome

### 3.4.3.3 Vaccine virus transmission

Presence of vaccine virus detected by RSVt qRT-PCR in nasal swabs after the second vaccination (D64 and D71) will be summarized in pediatric participants receiving placebo with 95% CIs:

- Number and percentage of participants with vaccine virus detected at each timepoint
- Number and percentage of participants with vaccine virus detected in at least one nasal swab

Transmissibility analyses will be performed on the SafAS. Vaccine virus transmission is defined in [Section 4.2.1](#).

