4.3 Justification for Dose

Justification for 2 doses administration schedule

There are several published studies evaluating 2 or 3 administrations of attenuated RSV or parainfluenza virus type 3 (PIV3) candidate vaccines (4) (5) (8) (24) (25) (26) (27) (28) (29). Generally, there was a high level of restriction of the second administration, and limited serum immune responses. The main effect was vaccine infectivity in the individuals who did not respond to the first administration. Two administrations of RSV Δ NS2/ Δ 1313/I1314L may improve the infectivity of either dose.

Justification for vaccine dose

The vaccine dose has been selected based on benefit/risk assessment based on results obtained the first Phase I/II VAD00001 study conducted in infants and toddlers 6 to 18 months of age receiving 2 doses of RSVt vaccine at concentration of [REDACTED]

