### 3.3 Populations for Analyses

For the purposes of analysis, the following analysis sets are defined:

Participant Analysis Set	Description
Randomized	Pediatric participants for whom a study intervention group has been allocated.
Safety Analysis Set (SafAS)	Pediatric participants who have received at least one study intervention administration. All pediatric participants will have their safety analyzed after each vaccination according to the study intervention they actually received, and after any vaccination according to the study intervention received at the first study intervention administration.  Safety data recorded for a vaccine received out of the protocol design will be excluded from the analysis (and listed separately).
Full Analysis Set (FAS)	Subset of randomized pediatric participants who received at least one study intervention administration.  Pediatric participants will be analyzed according to the study intervention to which they were randomized.

Per-protocol analysis set (PPAS)	
The PPAS is a subset of the FAS.
 
The pediatric participants presenting with at least one of the following relevant protocol deviations will be excluded from the PPAS:
 

• Pediatric participant did not meet all protocol-specified inclusion criteria or met at least one of the protocol-specified exclusion criteria

• Pediatric participant did not receive first study intervention administration at D01

• Pediatric participant received a study intervention at D01 other than the one that he / she was randomized to receive

• Preparation and / or administration of study intervention at D01 not done as per-protocol

• Pediatric participant NOT having at least 4 nasal swabs (with a valid result) between D08 and D22, with a maximum of 5 days' time interval between 2 consecutive nasal swabs

• Pediatric participant received a protocol-prohibited therapy before collection of nasal swab between D08 and D22

• Pediatric participant with an emergency unblinding performed by the investigator before collection of nasal swab at D22

• Pediatric participant who was RSV- exposed before study intervention administration at D01

Other analysis set	An analysis set will be used to document transmission of vaccine virus in the ad-hoc close contact participants

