order to provide geometric mean titers (GMTs) and geometric mean titers ratios (GMTRs) and their 95% CI.

$$GM \text{ is defined as follows: } GM = \left( \prod_{i=1}^n y_i \right)^{1/n} = 10^{\left( \frac{1}{n} \sum_{i=1}^n \log_{10}(y_i) \right)},$$

where  $(y_1, y_2, \dots, y_n)$  are the observed titers or individual ratios for each participant.

Viral shedding, vaccine virus stability (for pediatric participants receiving placebo and ad-hoc close contact participants), and safety analyses will be performed on the SafAS. Immunogenicity analyses and infectivity analyses will be presented on the FAS. Transmissibility analyses will be performed on the SafAS and PPAS as well as on other analysis set (ad-hoc close contact participants).

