### 4.2 Complementary Information on Derived Endpoints: Calculation Methods

#### 4.2.1 Vaccine Virus Transmission

Vaccine virus transmission is defined as presence of detected vaccine virus confirmed by RSVt qRT-PCR assay (vaccine virus shedding  $\geq$  LOD) in pediatric participants receiving placebo and ad-hoc close contact participants.

Detected viable RSV virus is defined as values from the plaque assay  $\geq$  LOD.

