## 6.2 Appendix 2 Use the Reed-Frost models and Greenwood models to estimate the transmission probability.

The binomial model is often used to estimate the transmission probability based on the idea that exposure to infection occurs in discrete contacts. Generally,  $p$  is defined as the transmission probability during a contact between a susceptible person and an infectious person. The quantity  $q = 1 - p$  is the probability that the susceptible person will not be infected during the contact, called the escape probability. In this section, the susceptible person is considered the pediatric participant who received placebo, and an infectious person is considered the pediatric participant who received RSVt vaccine.

Chain binomial models are dynamic models developed from the simple binomial model by assuming that infection spreads from individual to individual in populations in discrete units of time, producing chains of infection governed by the binomial probability distribution. The Reed-Frost and Greenwood models are examples of chain binomial models. To use these models, the number of susceptible persons and the number of infectious persons involved in each transmission generation should be known. However, in this study, the actual transmission chains is not observed, thus a single transmission generation is considered.

A contact group is defined as a group of pediatric participants who live in the same household or who attend in the same daycare center. A contact group is considered as a transmission unit and different contact groups are assumed to be separate and independent of one another. A total of  $J$  contact groups is assumed.  $S_j$  and  $I_j$  are the number of pediatric participants who received placebo and the number of pediatric participants who received RSVt vaccine in the  $j$ th contact group, respectively.  $X_j$  is the total number of pediatric participants who received placebo and have detective vaccine virus in the  $j$ th contact group.

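### Placebo children who already had vaccine virus detected after dose 1 remain full susceptibles in the dose-2 transmission analysis, so the dose-2 probability in susceptible children may be underestimated, increasingly so as dose-1 transmission rises

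*SAP*

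**What the plan says.** **Denominator.** For the secondary transmission endpoint, SAP 3.4.3.3 states that vaccine virus "in nasal swabs after the second vaccination (D64 and D71) will be summarized in pediatric participants receiving placebo". The set is given as "Transmissibility analyses will be performed on the SafAS", and SAP 3.3 defines the SafAS as "Pediatric participants who have received at least one study intervention administration". Neither removes a child for a positive swab after dose 1.

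**Event.** SAP 4.2.1: "Vaccine virus transmission is defined as presence of detected vaccine virus confirmed by RSVt qRT-PCR assay", at or above the LOD, in placebo recipients and ad-hoc contacts. A first detection is not required.

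**Model.** SAP 3.4.5 runs the Greenwood and Reed-Frost models after each administration. Appendix 2 notes: "To use these models, the number of susceptible persons and the number of infectious persons involved in each transmission generation should be known". It then sets S_j to all placebo recipients and I_j to all vaccinees in the contact group, treats a single generation, and gives no separate definition for dose 2.

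**Prior exposure.** The PPAS excludes a "Pediatric participant who was RSV- exposed before study intervention administration at D01". That rule is tied to D01. SAP 3.4.1 assigns transmissibility to both the SafAS and the PPAS, but 3.4.3.3 names only the SafAS.

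**Biology.** Protocol 4.3, on earlier studies of two or three doses of attenuated RSV or PIV3 vaccines: "Generally, there was a high level of restriction of the second administration, and limited serum immune responses". It adds that a second dose mainly infected those who had not responded to the first. Protocol 4.2 expects infants with earlier RSV infection to shed less.

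**The concern.** A placebo child who acquires vaccine virus between D01 and D22 has in effect had a first dose by contact. On the protocol's own reasoning such a child is likely to be harder to infect after dose 2, yet counts as fully at risk in the 3.4.3.3 denominator and in S_j. The plan acts on prior exposure at dose 1, through the PPAS, but its rule cannot reach exposure that arises in the trial after D01.

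The model is where this matters most, because its parameter is a probability per contact for a susceptible child. Transmission after dose 2 is a named secondary objective in a study meant to inform a large Phase III trial. The protocol already expects less shedding after dose 2, so an estimate that is low partly because of its denominator could be read as confirmation.

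**Working it through.** **Inputs.** 50 placebo recipients (SAP 3.2), swabs at D04–D22 after dose 1 and at D64 and D71 after dose 2, and Clopper-Pearson intervals (SAP 3.4.1). The documents give no transmission rate, no relative susceptibility and no contact-group sizes, so those below are assumptions shown as ranges. There is no planned figure to reproduce, since SAP 3.2 makes no sample size calculation. Appendix 2's example (two placebo, three vaccinees) is coherent: at q=0.9, both escape with probability q^6 = 0.531 and both are infected with probability (1−q^3)^2 = 0.073.

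**1. Crude rate.** Let x be the placebo children positive after dose 1, p2 the dose-2 probability in a susceptible child, and r the relative susceptibility of the x children. In one-to-one pairs the expected number of dose-2 detections is (50−x)·p2 + x·r·p2. Dividing by 50 gives p2·[1 − (x/50)(1−r)], so the relative shortfall is (x/50)(1−r). With p2 = 10%:

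| x | r=0 | r=0.5 | r=1 |
|---|---|---|---|
| 0 | 10.0% | 10.0% | 10.0% |
| 1 | 9.8% (2% low) | 9.9% (1% low) | 10.0% |
| 5 | 9.0% (10% low) | 9.5% (5% low) | 10.0% |
| 10 | 8.0% (20% low) | 9.0% (10% low) | 10.0% |

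**2. Models.** Maximising the Greenwood likelihood gives ΣX_j/ΣS_j, which is the crude rate, so it carries the same shortfall. In pairs I_j = 1 and Reed-Frost reduces to the same estimate. For larger groups, Reed-Frost was simulated (1,000 runs) with an assumed mix of 30 pairs, four groups of 2+2 and four of 3+3 (30+8+12 = 50 placebo children). The true dose-2 p was 0.10, and p1 is the dose-1 probability per contact:

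| p1 | Share positive after dose 1 | S_j as written, r=0 | S_j as written, r=0.5 | S_j reduced, r=0 |
|---|---|---|---|---|
| 0.02 | 3.2% | 0.096 | 0.097 | 0.101 |
| 0.05 | 8.1% | 0.089 | 0.095 | 0.099 |
| 0.10 | 15.5% | 0.080 | 0.093 | 0.100 |
| 0.20 | 29.5% | 0.063 | 0.084 | 0.100 |

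Here S_j reduced means that dose-1 positives are removed from both S_j and X_j. At r=0 and p1 = 0.10 the shortfall is 20%, against 15.5% of placebo children positive after dose 1. It exceeds that share because dose-1 infections fall more often in groups with more vaccinees.

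**3. Does the observed rate fall?** Only if p2 stays fixed. If instead p2 = p1, with r=0 and pairs, the expected crude rate is p1(1−p1): 2.0%, 4.75%, 9.0%, 16.0% and 21.0% for p1 = 2%, 5%, 10%, 20% and 30%. It rises, and turns down only above p1 = 50%. What grows throughout is the shortfall against p2.

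**4. Cost in precision.** With zero events the upper 95% limit is 7.1% for 0/50, 7.9% for 0/45 and 8.8% for 0/40. With two events the estimates are 4.0% (0.5–13.7) of 50, 4.4% (0.5–15.1) of 45 and 5.0% (0.6–16.9) of 40.

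**The case against.** The case for leaving the plan alone has real weight.

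- **The endpoint matches its objective.** The objective is to describe transmission in placebo recipients after the second administration, and the percentage of all of them does so. Conditioning on a post-randomization result answers a different question. This stands: the all-placebo line is not an error.
- **The premise is not quantified.** A reader might infer that a dose-1 positive child is no longer susceptible at all. The documents do not say so. Protocol 4.3 concerns a second direct dose, Protocol 4.2 concerns shedding, and a positive is any qRT-PCR result at or above the LOD, with viable virus defined separately by plaque assay. This stands, and is why r is carried as an unknown.
- **S_j is a declared convention.** Appendix 2 says openly that the placebo recipient is taken as the susceptible person. It does, but it also says the number of susceptibles should be known for each generation, and dose 2 is where the two part company.
- **Susceptibility was never screened.** Children RSV-exposed at baseline stay in the SafAS, and wild-type infection may occur between doses. True, so the change removes one source of bias and not all of them. The source it removes is the one the trial itself creates and measures.
- **No comparison of doses is planned.** All analyses are descriptive, the model is exploratory, and six post-dose swabs against two would confound a comparison anyway. This limits the harm but does not correct the model's input.

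**Conclusion.** The point holds as a modest improvement. Children positive at D04–D22 remain in the dose-2 denominator and, as full susceptibles, in S_j. If they are less susceptible (r<1), the dose-2 probability in susceptible children is increasingly underestimated as dose-1 transmission rises, by (x/50)(1−r) in the crude rate.

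Two limits apply. A reader might infer that the dose-2 rate falls whenever dose 1 transmits more. That requires the dose-2 probability to stay fixed, which the documents do not establish; step 3 shows that the rate can rise. And the size may be trivial: nil if dose 1 shows no transmission, and at x=5 well inside the interval for 50 children. It becomes noticeable when about 10–20% or more of placebo children are positive after dose 1. The larger Reed-Frost shortfalls rest on r=0 and assumed group sizes. Without a D57 swab, carry-over shedding could act in the opposite direction, though the protocol does not expect it.

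**What to change.** - **Appendix 2.** For the dose-2 models, define S_j as placebo recipients in the contact group with no vaccine virus detected at D04–D22, and count X_j among those same children. A group left with S_j = 0 contributes nothing to the likelihood.
- **SAP 3.4.3.3.** Keep the all-placebo line. Add a line for placebo children with no vaccine virus detected at D04–D22, and list re-detections in the others separately. State how children without a valid D04–D22 swab are classified.
- **Analysis set.** Reconcile 3.4.3.3 (SafAS only) with 3.4.1 (SafAS and PPAS).

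The cost is SAP wording and a little programming on swabs already planned. The added line has a slightly smaller denominator and a wider interval. Reduced susceptibility from baseline RSV exposure or wild-type infection remains and should be acknowledged beside the estimate.
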